4.11.2 Deaths, Serious Adverse Events, and Other Significant Adverse Events

Other significant adverse events are those adverse events reported as leading to an intervention e.g. withdrawal from study, discontinuation of study treatment, introduction of concomitant medication, dose reduction. Following the specification provided for adverse AE summaries at section 4.11.1 summaries detailed below will be provided for deaths, SAEs and other significant AEs:

- Number and percentage of patients for each TEAE leading to death, categorized by SOC and PT
- Number and percentage of patients for each treatment-emergent SAE, categorized by SOC and PT
- Number and percentage of patients for each TEAE leading to study discontinuation, categorized by SOC and PT
- Number and percentage of patients for each TEAE leading to treatment withdrawal, categorized by SOC and PT

For deaths, SAEs and other significant AEs the following listings will be provided:

- A by-patient listing of all deaths that occurred during the study
- A by-patient listing of all serious treatment-emergent adverse events
- A by-patient listing of all TEAE leading to treatment withdrawal
- A by-patient listing of all TEAE leading to study discontinuation

4.11.3 Clinical Laboratory Evaluation

Laboratory values (hematology and biochemistry) will be summarized for all visits scheduled in treatment and follow up periods. Unscheduled visits will be listed only, unless contribute to baseline measurement.

The baseline for the laboratory values is defined as the last evaluable measurement before first dose, including any unscheduled assessment.

The Investigator will assess whether the values outside the clinical reference range are clinically significant and these will be reported as abnormal not clinically significant (NCS) or abnormal clinically significant (CS). Clinically significant laboratory values will be recorded by the Investigator as AEs.

Clinical laboratory parameters will be split into hematology and chemistry categories. The following summaries will be provided for all parameters:

- A summary of results by treatment group and visit.
- A summary of the change from baseline by treatment group and visit.
- Shift tables by treatment group and visit will be provided for all parameters to compare a patient's baseline laboratory evaluation relative to the visit's observed value. For the shift tables, the normal laboratory ranges will be used to evaluate whether a particular laboratory test value was normal, low, or high for each visit value relative to whether or not the baseline value was normal, low, or high.

By-patient listing will be provided for all patient enrolled by visit, including changes from baseline and reference range. All values outside the clinical reference ranges will be flagged in the data listings. The abnormal values will be flagged with 'L' for values below the lower limit of the clinical reference range and 'H' for values above the upper limit of the clinical reference range and included in the listings.

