5.2.2. Follow-up of out-patients between D0 and D14

After D0, outpatients will be contacted every other day by the investigator or his/her designee.

During this remote medical monitoring, outpatients will be questioned on their state of health, including body temperature, SPO2, clinical signs and occurrence of any potential adverse events as well as any change in the current medication will be checked. Data will be recorded in the patient's medical chart and in the dedicated page of the eCRF.

In case of any sign of worsening, outpatients will be asked to come back to the study site for an unscheduled visit where additional examinations will be performed.

During the last daily contact, the D14 onsite visit will be confirmed to the patient. Patients will be asked to bring back the oximeter provided at D0.

If no quarantine period is applied or if patient migration to the study site is acceptable as per local country regulation, outpatients will perform a D7 visit on-site where the same examinations as hospitalized patients will be done.

In case of quarantine policy, sites should organize home care settings to collect samples at D7 at patients' home.

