7.2. Patient Premature trial discontinuation

A patient can be withdrawn at any time from the study. Premature trial discontinuation could occur for the following reasons:

- Investigator's decision.
- An Adverse Event or an intercurrent condition that preclude continuation of treatment. Specifically, an elevation $\geq 3.0 \times$ ULN in liver transaminases (AST/SGOT and/or ALT/SGPT) or Alkaline phosphatase or in total bilirubin compared to baseline requires close observation with repeating liver enzymes and serum bilirubin tests every 2 days. Discontinuation of the study treatment should occur if:
 - ALT or AST $> 8 \times$ ULN
 - ALT or AST $> 3 \times$ ULN and total bilirubin $> 2 \times$ ULN or INR > 1.5
 - ALT or AST $> 3 \times$ ULN with appearance of fatigue, nausea, vomiting, right upper quadrant pain or tenderness, fever, rash, and/or eosinophilia ($> 5\%$).
 - Alkaline Phosphatase $\geq 2.0 \times$ ULN
- Serious adverse event with suspected causal relationship to the IMP
- Any relevant toxicity or negative change in the risk/benefit assessment leading to an unacceptable risk for the patient (i.e. occurrence of adverse events which character, severity or frequency is new in comparison to the existing risk profile), or any data deriving from other clinical trials or toxicological studies which negatively influence the risk/benefit assessment.
- Major protocol violation.
- Withdrawal of consent.
- Administrative reasons from Sponsor.

A patient who prematurely exits the study will not be replaced.

All patients, regardless of the completion or premature discontinuation, should come back for an on-site safety follow-up visit 21 days after the last study drug intake, and all examinations must be performed according to the study flow-chart.

The same long-term follow-up will be performed as described in section 7.1 providing the reason for premature discontinuation is not "withdrawal of consent".

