9.2. Safety Analyses

Adverse events will be coded using the standard dictionary (MedDRA) down to the lower level term (LLT).

An overall summary table will be presented (Any adverse event, any treatment emergent adverse event (TEAE), any serious adverse event (SAE) including serious adverse drug reactions (SARs) and suspected unexpected serious adverse reactions (SUSARs), death, any grade 3 or higher adverse events from baseline to the end of Study).

Two periods will be defined for TEAE:

- Any adverse event which occurs or worsens from first dosing to Day 28;
- Any adverse event which occurs after Day 28.

TEAEs will be described by primary system organ class and preferred term. Numbers and percentage of patients, and number of occurrences of adverse event will be presented for:

- TEAE;
- Serious TEAE;
- TEAE leading to study treatment discontinuation;
- TEAE of grade 3 or 4;
- TEAE for which relationship with the study treatment is recorded as possible or probable.

The assessment of safety will be based on the frequency of adverse events (with and without regard to causality) graded according to the CTC-AE Classification (version 5.0) and also, the review of individual values for clinical laboratory data, vital signs and ECG focusing on the detection of abnormal values and PCSAs [potentially clinically significant abnormalities (PCSAs) determined upon investigator considerations].

Clinical laboratory parameters, vital signs, ECG will be summarized by using descriptive statistics (n, mean, SD, median, minimum and maximum). Number of patients with at least one abnormal value will be tabulated (counts and percentages) for each parameter in summary shift tables, by study treatment group.

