4.2.3 Analysis Periods, Visit Windows and Naming

Analysis periods will be derived for the statistical analyses based on the assigned analysis visits. Timing of analysis periods with start and end visits are tabulated in [Table 1](#).

Table 1 Analysis Periods

Analysis Period	Start	End
Treatment Period	Visit 1 (Day 1)	Visit 5
Safety Follow-up Period	Visit 5 + 1 day	Visit 6
Long-term FUP	Visit 6 + 1 day	Visit 7
Overall Study Period	Visit 1 (Day 1)	Visit 7

As patients will not necessarily have their examinations at the exact scheduled visit time, it could be misleading if all data with the same nominal visit number are lumped together for a by-visit analysis. Thus, all post-baseline data (including both scheduled and unscheduled visits) will be “realigned” in the statistical analysis according to the appropriate window schema and according to the following general conventions.

The reference start day of the first visit window in the Treatment Period is Day 1. The start day of all other visit windows up to Visit 5 (Day 28) is the midpoint between the scheduled visit day for the previous visit ($Visit_{(i)}$) and the subsequent visit ($Visit_{(i+1)}$) plus 1 day: $(Visit_{(i)} + Visit_{(i+1)})/2 + 1$.

The end day of a visit window in the Treatment Period is the day prior to the start day of the next visit window with the exception of the last visit window, where the end day of the visit window will be the day of the EoT visit.

Safety Follow-up Period: Visit 6 (EoS) and Visit 7 (Long term FUP) assessments will be realigned utilizing the same general conventions but with the reference start day of the safety follow-up period derived relative to the last available assessment (scheduled or unscheduled) assigned to Treatment Period + 1 day (see [Table 2](#)).

Width of a realigned visit window will depend on the schedule of assessments for the respective type of assessment. That is, $Visit_{(i)}$ and $Visit_{(i+1)}$ day above refer to the visits as scheduled for the respective assessment and unless otherwise specified will be realigned per [Table 2](#) (General realignment of visits).

Multiple assessments within visit windows

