4.11.4 Vital Signs, Physical Findings and Other Observations Related to Safety

Vitals signs, ECG recording will be summarized for all visits scheduled in treatment and follow up periods. Unscheduled visits will be listed only, unless they contribute to baseline measurement.

Baseline is defined as the last evaluable measurement before first dose, including any unscheduled assessment.

Vital Signs

Following vital signs will be measured:

- Systolic blood pressure [mmHg]
- Diastolic blood pressure [mmHg]
- Pulse rate [beats/min]
- Body temperature (oral, tympanic or rectal) [°C or °F]
- Oxygen Saturation [%]

Investigators will assess each vital sign value and categorize either as clinically significant (CS) or not clinically significant (NCS).

Temperature values recorded as °F will be summarized as °C using the function below:

$$^{\circ}\text{C} = (^{\circ}\text{F} - 32) \times \frac{5}{9}$$

For body temperature measurements in degrees of Fahrenheit, both $^{\circ}\text{F}$ and $^{\circ}\text{C}$ values and units will be reported in line listings. Body temperature values obtained from different body parts will be summarized separately by measurement location in the order of oral, tympanic and rectal.

The following summaries for vital signs will be provided:

- A summary of each vital sign along with number and percentage of patient with CS vital sign by treatment group and visit.
- A summary of the change from baseline in each vital sign parameter by treatment group and visit.
- A summary of the number and percentage of patients with any CS vital sign value in each vital sign parameter by treatment group.

By-patient listing will be provided for all patient enrolled by visit, including changes from baseline and investigator's interpretations. A separate listing of potentially clinical important vital signs will be provided for assessments with any CS vital sign observation.

ECG

For each time point, an overall interpretation will be recorded by the Investigator as normal, abnormal not clinically significant, or abnormal clinically significant.

A summary of the number and percentage of patients in each category (normal, abnormal NCS and abnormal CS) will be provided by treatment group and visit.

By-patient listing will be provided for all patients enrolled. A separate listing of potentially clinical important ECG readings will be provided for ECG recordings assessed as CS.

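### The SAP plans no count of patients with at least one abnormal laboratory or ECG value, which Protocol 9.2 commits to, and its listing-only rule for unscheduled visits would make such a count too low

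*SAP*

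**What the plan says.** Protocol 9.2 (Safety Analyses) names laboratory parameters, vital signs and ECG, and then commits to this for each arm: "Number of patients with at least one abnormal value will be tabulated (counts and percentages) for each parameter in summary shift tables". The synopsis repeats the commitment.

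For laboratory data, SAP 4.11.3 says: "Laboratory values (hematology and biochemistry) will be summarized for all visits scheduled in treatment and follow up periods". It then says: "Unscheduled visits will be listed only, unless contribute to baseline measurement". The tables it lists are results by visit, change from baseline by visit, and shifts in low/normal/high categories: "Shift tables by treatment group and visit will be provided for all parameters".

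For vital signs and ECG, SAP 4.11.4 has the same restriction: "Unscheduled visits will be listed only, unless they contribute to baseline measurement". ECG interpretation is tabulated by treatment group and visit only. Vital signs also get a per-patient count of any clinically significant value by treatment group. Laboratory and ECG data have no equivalent.

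SAP 4.2.3 gives a different general rule: "all post-baseline data (including both scheduled and unscheduled visits) will be" realigned to visit windows, with the record closest to the target day analysed.

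On when unscheduled tests arise, Protocol 5.2.2 says: "In case of any sign of worsening, outpatients will be asked to come back to the study site for an unscheduled visit". Protocol 5.2.8 includes ECG, hematology and biochemistry in such a visit. Protocol 7.2 says that a rise in liver tests to its stated level "requires close observation with repeating liver enzymes and serum bilirubin tests every 2 days".

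**The concern.** SAP version 5.0 drops efficacy, so safety is all that remains to report. A per-patient count by arm is the simplest laboratory safety summary, and the protocol committed to it. Ending the efficacy analyses does not explain its absence, and SAP 4.13, which lists the changes to the planned analysis, does not mention it. The vital-sign count in 4.11.4 suggests an oversight.

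The rule on unscheduled visits matters because those visits are not a random sample of days. Some take place because the patient has got worse, so a by-arm table that leaves them out omits tests taken when an abnormal result is most likely. The protocol also reports liver findings in animal studies and adds a specific liver monitoring plan (1.5), so the size of liver-test peaks is of interest even though it reports no hepatotoxicity in treated patients.

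**Working it through.** No sample size, power or error rate is involved, and the plan states no figure to reproduce. The check is a comparison of texts plus a day count.

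**1. Can the promised count be read from the by-visit tables?** Suppose *a* patients in an arm are high on a parameter at Day 14 and *b* at Day 21. The number high at least once over those two visits lies anywhere from max(*a*, *b*) to *a* + *b*, because the same patient may appear at both. The by-visit tables give *a* and *b* but not the overlap. The count is therefore missing because the tables are by visit, and it would be missing even if no patient had an unscheduled test.

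**2. Which tests does the listing-only rule exclude?** Outpatient visits for worsening are unscheduled by the protocol's own words (5.2.2, 5.2.8). The 2-day liver repeats are not expressly called unscheduled. That follows from 5.2.8 only if they are done on site between two on-site visits.

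**3. What would a scheduled-only count lose?**
- If the first abnormal value is at a scheduled visit, the patient is counted. Leaving out the repeats loses the peak, not the patient.
- If every abnormal value is at an unscheduled visit, the patient is not counted.

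The count can therefore only be too low, by the number of patients in the second group.

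**4. Would following SAP 4.2.3 cure this?** Assume a liver-test rise on Day 7, repeats every 2 days to Day 28, and scheduled visits on target at Days 7, 14, 21 and 28. The repeats on non-scheduled days are 9, 11, 13, 15, 17, 19, 23, 25 and 27, nine in all. SAP Table 2 gives windows of Days 2–10, 11–18, 19–25 and 26 to drug return.

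| Window (target) | Records available | Selected |
|---|---|---|
| 2–10 (7) | 7, 9 | 7 |
| 11–18 (14) | 11, 13, 14, 15, 17 | 14 |
| 19–25 (21) | 19, 21, 23, 25 | 21 |
| 26 on (28) | 27, 28 | 28 |

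Under 4.11.3 none of the nine is tabulated. Under 4.2.3 none is selected.

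The result under 4.2.3 depends on the scheduled visits being on target. SAP 4.2.1 calls Visit 1 Day 1, so visits exactly 7, 14, 21 and 28 days later fall on SAP Days 8, 15, 22 and 29. Repeats every 2 days from Day 8 then fall on nine non-scheduled days: 10, 12, 14, 16, 18, 20, 24, 26 and 28. The closest-record rule picks Day 8, Day 14, Day 20 (tied with Day 22, and the earlier is taken) and Day 28. Three of the nine enter, in place of scheduled records, and six do not. In both cases one record per window is kept for its date, not its severity, so a between-visit peak is usually dropped.

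**5. What still reaches a by-arm table?** Clinically significant laboratory values are recorded as adverse events (SAP 4.11.3), and clinically relevant ECG changes likewise (Protocol 5.3.4), whatever the visit type. They enter the treatment-emergent tables, including maximum CTCAE grade. Abnormal values not judged clinically significant reach only the listings, where laboratory values are flagged high or low.

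**The case against.** The best defence is that nothing is lost from the database. Every out-of-range laboratory value is listed and flagged by patient, so the count can be derived at any time. A reader might infer that the SAP makes the count impossible. It does not; it fails to plan it. That part of the defence stands. A listing is still not the by-arm tabulation that Protocol 9.2 commits to.

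The adverse event tables are a real safeguard, and they narrow the loss to abnormal values not judged clinically significant and the height of peaks. They do not replace the count, because Protocol 9.2 refers to abnormal values without a clinical-significance condition.

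The windowing text in 4.2.3 contains an exception for cases specified otherwise, so 4.11.3 and 4.11.4 can be read as the specific rule. That reading is reasonable, but the SAP does not say so, and two programmers could build different tables from it.

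A reader might also try to size the problem by how often a short abnormality falls between weekly visits. That measures abnormalities never sampled, which no choice of table can recover. Only values actually measured at unscheduled visits are at issue. Nor do the documents show that a difference between arms would be hidden: the undercount applies to both arms, and nothing indicates how it would differ between them.

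**Conclusion.** The point holds in a limited form. A by-arm, per-patient count that the protocol commits to is not planned for laboratory or ECG data, and its omission is not declared in SAP 4.13. The by-visit format is the main cause. The listing-only rule is a second defect that would make any count built on it too low, and the SAP's two rules on unscheduled data have not been reconciled.

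The size cannot be given as a number, because the documents report no frequency of unscheduled tests. Its scope can be stated: abnormal values not judged clinically significant, and peak values between visits. The worsening-triggered part rests on explicit protocol text. The liver-repeat part assumes that the repeats are done on site. The day count assumes a Day 7 rise (Day 8 in the shifted case), repeats every 2 days and the stated visit days. It shows how the rules work and does not estimate a rate.

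**What to change.** In SAP 4.11.3 and 4.11.4 add, by treatment group and using scheduled and unscheduled post-baseline results:

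- the Protocol 9.2 count and percentage of patients with at least one abnormal value, for each laboratory parameter and for ECG;
- a shift table from baseline to worst post-baseline value for each laboratory parameter, low and high separately;
- the worst post-baseline ECG category per patient.

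State that by-visit tables use scheduled visits only, and amend 4.2.3 so that it agrees with 4.11.3 and 4.11.4. If the sponsor prefers not to produce the count, declare the omission in 4.13.

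A by-arm count of patients meeting each liver threshold already written in Protocol 7.2 is optional. Protocol 9.2 does not require it, but it would help because low/normal/high shifts do not show how high a peak was.

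The cost is some SAP wording and a few extra tables in an abbreviated report. No new data are needed and patient management does not change.

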- Number and percentage of patients for each TEAE, categorized by system organ class (SOC) and preferred term (PT)
- Number and percentage of patients for each TEAE of grade 3 or higher, categorized by SOC and PT
- Number and percentage of patients for each TEAE occurring in $\geq 5\%$ of subjects in any treatment group, categorized by SOC and PT
- Number and percentage of patients for each TEAE, categorized by SOC, PT, and maximum CTCAE grade
- Number and percentage of patients for each TEAE, categorized by SOC, PT, and relationship to study drug
- Number and percentage of patients for each TEAE of grade 3 or higher, categorized by SOC, PT, and relationship to study drug
- Number and percentage of patients for each treatment-emergent SAE, categorized by SOC, PT, and relationship to study drug

Adverse event summaries will be ordered in terms of decreasing frequency for SOC and PT within SOC in the Total group and then alphabetically for SOC and PT within SOC. Summaries will be ordered in terms of decreasing frequency for PT in the Total group in summaries where SOC is not included.

For each patient and each adverse event, the worst severity (highest CTCAE grade) recorded will be attributed and used in the by-severity summaries. Similarly, the worst causality (most related to treatment) will be attributed and used in the by-causality summaries. If CTCAE grade or causality is missing, a conservative approach for AE assessment (taking into account the worst case) will be followed.

A by-patient listing of all adverse events (including non-treatment-emergent events) will be provided. This listing will be presented by dose and will include patient identifier, age, sex, race, adverse event (SOC, PT, and verbatim term), date of onset, date of resolution, duration, severity, seriousness, outcome action taken (concerning both action with study drug and primary action (not related to study treatment)) and causality (concerning both study treatment and non-study treatment).

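### No laboratory summary specified in the SAP counts patients by arm at the protocol's ULN-multiple liver levels, and a peak at an unscheduled retest can be missing from the tables

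*SAP*

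**What the plan says.** **Laboratory tables.** SAP 4.11.3 plans three summaries by arm and visit: results, change from baseline, and a shift table. For the shift table, "the normal laboratory ranges will be used to evaluate whether a particular laboratory test value was normal, low, or high for each visit value". On other values it says "Unscheduled visits will be listed only, unless contribute to baseline measurement". It also provides a listing: "By-patient listing will be provided for all patient enrolled by visit, including changes from baseline and reference range". Listed values outside the range are flagged low or high.

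**Adverse event tables.** SAP 4.11.3 gives the route from a laboratory value to an adverse event: "Clinically significant laboratory values will be recorded by the Investigator as AEs". SAP 4.11.1 plans "Number and percentage of patients for each TEAE, categorized by SOC, PT, and maximum CTCAE grade", and SAP 4.11.2 plans "Number and percentage of patients for each TEAE leading to treatment withdrawal, categorized by SOC and PT".

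**Liver levels.** Under Protocol 7.2, a rise of at least 3× ULN in transaminases or alkaline phosphatase (ALP), or "in total bilirubin compared to baseline requires close observation with repeating liver enzymes and serum bilirubin tests every 2 days". It continues "Discontinuation of the study treatment should occur if" and gives four rules: ALT/AST >8×; ALT/AST >3× with bilirubin >2× or INR >1.5; ALT/AST >3× with listed symptoms or eosinophilia; ALP ≥2×.

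**Background.** Protocol 1.5 names the liver as a main target organ in animals, reports no hepatotoxicity in treated patients, and adds liver monitoring to this study all the same.

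**The concern.** The levels that govern patient management are ULN multiples, while the tables are cut at 1× ULN. A trivial rise and one past a stopping level therefore land in the same shift cell. The retests that a large rise triggers are the kind of value that SAP 4.11.3 keeps out of the tables.

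After the futility stop, SAP 2.2 and 4.13 remove every objective except safety. For the one organ with its own monitoring plan, the specified tables would show average changes, extremes and investigator-judged events. They would not show, by arm, how many patients reached the observation or stopping levels, or had a combined ALT/AST and bilirubin or INR rise.

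**Working it through.** The plan states no figure to reproduce. The check sets each protocol level against each specified output.

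**Step 1. Does any specified output count the level by arm?**

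| Protocol 7.2 criterion | Laboratory tables (SAP 4.11.3) | Adverse event tables (SAP 4.11.1, 4.11.2) |
|---|---|---|
| Observation: ≥3× for ALT/AST, ALP or bilirubin | No; shown as high | Only if judged clinically significant |
| Stop: ALT/AST >8× | No; shown as high | Yes, if the stop is made and recorded as an event; by event term, not by level |
| Stop: ALT/AST >3× with bilirubin >2× or INR >1.5 | No; each test is tabulated separately | As above |
| Stop: ALT/AST >3× with symptoms or eosinophilia | No | As above |
| Stop: ALP ≥2× | No; shown as high | As above |

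Criteria counted in a laboratory summary: 0 of 5.

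**Step 2. What the shift table can and cannot separate.** This is an illustration with assumed values. Take 100 patients in one arm, all at 0.6× ULN at baseline. At a scheduled visit 95 stay there and 5 rise to *t*. Mean change = 5 × (*t* − 0.6) / 100.

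| *t* (× ULN) | Normal→normal | Normal→high | Mean change (× ULN) | Maximum (× ULN) | Count ≥3× | Count >8× |
|---|---|---|---|---|---|---|
| 1.2 | 95 | 5 | 5 × 0.6 / 100 = 0.03 | 1.2 | 0 | 0 |
| 3.5 | 95 | 5 | 5 × 2.9 / 100 = 0.145 | 3.5 | 5 | 0 |
| 9 | 95 | 5 | 5 × 8.4 / 100 = 0.42 | 9 | 5 | 5 |

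The shift table is identical in all three cases. The mean and maximum respond but give no count of patients. The SAP states no scaling to ULN, so its summaries would be in recorded units; the ULN scale here assumes one common ULN. Entry criteria allow ALT/AST up to, but below, 3× ULN (Protocol 4.2.1), so a patient going from 1.5× to 9× would be high→high.

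**Step 3. What happens to retest values.** Protocol 5.2.8 defines an on-site visit between two on-site visits as unscheduled, and biochemistry is drawn there. Suppose a patient has ALT 3.5× at the Day 14 visit and 9× at a retest on Day 16 (assumed values).

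- Under SAP 4.11.3 the retest is unscheduled and listed only, so the tables carry 3.5×.
- SAP 4.2.3 conflicts with this: it realigns unscheduled post-baseline data into visit windows. Days 14 and 16 both fall in the Visit 3 window (Days 11 to 18, target Day 14). The record nearest the target day is kept, so the tables again carry 3.5×.

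The two rules differ, but neither selects the worst value.

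**The case against.** **Protocol 9.2 plans review of individual laboratory values.** This stands. The SAP listings serve that review, with reference ranges, changes from baseline and flags, and they include unscheduled values. Nothing is lost. But the flags mark only low or high, so a comparison of arms at 3× or 8× has to be counted by hand.

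**The serious cases are already counted.** This largely stands. A patient stopped under Protocol 7.2 should appear in the treatment-withdrawal table, and graded events are tabulated by arm. Grade 3 or higher events also go to the DSMB within 24 hours (Protocol 3.2, 3.3). A reader might infer that severe liver cases go uncounted; the documents do not support that. What remains is mainly the patient at the observation level, or judged not clinically significant. In Step 2, the 3.5× patients without symptoms, eosinophilia, raised bilirubin or raised INR enter an adverse event table only on the investigator's judgement.

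**The protocol asks for no such table.** Correct. Protocol 9.2 and 9.4 plan descriptive statistics and shift tables and mention no ULN multiples. Reading this as the SAP breaking a protocol commitment would be wrong.

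**Missed days.** A reader might take the gaps between the protocol's ±2-day visit tolerances as days on which a peak is lost. The documents do not support that. Exclusion under SAP 4.11.3 turns on visit type, not calendar day: a scheduled visit held late is still tabulated, and an unscheduled retest inside a tolerance is not. The SAP Table 2 windows run on without gaps through treatment into safety follow-up. A first value ≥3× found at a scheduled visit is also in the tabulated data; only later retest peaks can drop out.

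**Output shells.** SAP 4.11.5 refers to table shells that are not among the documents. They may contain more, so the finding concerns only what the SAP text specifies.

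**Conclusion.** The point holds as an improvement to the choice of table. The SAP text specifies no laboratory summary that counts patients by arm at any of the five Protocol 7.2 liver criteria. A peak at an unscheduled retest can be absent from the tables under either SAP 4.11.3 or SAP 4.2.3.

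The practical size is limited. Cases judged clinically significant or acted on are counted through the adverse event tables, and the rest can be recovered from the listings. How many patients that is cannot be known from the documents, and the 5 in 100 in the illustration is assumed. No estimate, test or decision rule changes. Nor do the documents indicate a liver signal: Protocol 1.5 reports none in treated patients. A table of zeros by arm would support that statement directly, and a table with counts would qualify it.

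The conclusion assumes that the stopping rules are followed and recorded as events, and that the unseen shells add no such table.

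**What to change.** In SAP 4.11.3 add one table by actual arm on the Safety Set, using each patient's worst post-dose value, scheduled or unscheduled, as a multiple of the local laboratory's ULN. Show n (%) for:

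- ALT/AST ≥3×, >3× and >8×;
- ALP ≥2× and ≥3×;
- bilirubin >2× and ≥3×;
- ALT/AST >3× with bilirubin >2×, or with INR >1.5 where INR was measured.

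Show these by baseline multiple, because the observation trigger is worded relative to baseline. Add a listing of patients with ALT/AST >3× or any laboratory stopping level, to be read against their adverse events and eosinophil counts for the symptom rule. State that this table uses the worst value whichever of SAP 4.2.3 and 4.11.3 governs the by-visit tables, and settle which of the two does.

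**Cost.** One table and one listing, from values and reference ranges that the SAP already lists; no new data. INR will be missing where the local laboratory reported only prothrombin time (Protocol 5.3.7, Table 2), so the INR part of the combined criterion needs its own denominator.
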